## 2.3 Clinical Experience of Dorgenmeltucel-L (HyperAcute Melanoma)

In the phase 1 dorgenmeltucel-L Trial NLG0104, 6 subjects received the melanoma immunotherapy. Six patients, 2 men and 4 women, mean age- 60 years (range, 36-76), were vaccinated with one priming dose of 500 million cells and up to eleven booster doses of

300 million cells. Observed events unrelated or unlikely to be related to the immunotherapy included Grade 1 fatigue, pruritus, nausea, vomiting, constipation, dysphagia, dermal change, facial edema, hyperglycemia, pain, and nocturia. Grade 1 events possibly related to the immunotherapy included fatigue, nausea, and dysgeusia. Grade 2 events unrelated or unlikely related to the immunotherapy include pruritus, cellulitis, left hemianopsia, and headache. One Grade 3 cellulitis was observed after a brown recluse spider bite in one of the subjects. Events probably or definitely related to the immunotherapy include Grade 1 and 2 injection site reactions to include redness, swelling, and itching. Five of the six patients went off study, 3 due to progression of disease and 2 due to concurrent illness. One subject remains on long-term follow-up with stable disease (> 5 years).

Riker *et al.* have since completed a phase 2 clinical trial of dorgenmeltucel-L (NLG12036, NewLink Genetics) combined with pegylated interferon (Sylatron™, Merck). Trial design consisted of a 12-week regimen with the initial 4 weekly treatments consisting of dorgenmeltucel-L alone (intradermally) followed by 8 additional treatments of dorgenmeltucel-L plus Sylatron™ (subcutaneously, 6 µg/kg). Trial endpoints include clinical response, overall safety and correlative findings for observed anti-tumor effect. They report a total of 25 patients accrued with a median age 60, 68% male with 21 patients completing the trial, 4 stopped due to progressive disease (PD).

By RECIST criteria, of 16 Stage IV patients, there were 2 complete responders (CR), 1 with stable disease (SD) and 4 with no evidence of disease (NED) after resection. For Stage III patients, 4/9 remains NED, 1 patient with slowly progressive disease with a single site resected and currently NED. The median overall survival is 29 months, with 60% of the patients surviving for >1 year and 12/25 (48%) still alive. All evaluable patients (21/21) seroconverted, developing autoimmune antibodies. Vitiligo developed in 4/25 patients, correlating with 2 CR and 2 NED.

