### 10.4 *Definitions for Reporting Purposes*

In this protocol the study drug dorgenmeltucel-L is being combined with one of three different immune checkpoint immunotherapies, drugs with an established safety profile. Adverse events and serious adverse events observed during the course of this trial and previously reported as related to ipilimumab, nivolumab, or pembrolizumab will be attributed to such. Adverse events previously seen with dorgenmeltucel-L or other HyperAcute therapies will be attributed to dorgenmeltucel-L. Novel serious adverse events not previously seen with any study agent will initially be considered regimen associated and will require an evaluation by the PI and the sponsor

to determine attribution. This will be done via teleconference within three business days of the report.

An **adverse event** (AE) is any symptom, sign, illness or experience that develops or worsens in severity during the course of the study. Intercurrent illnesses or injuries should be regarded as adverse events. Abnormal results of diagnostic procedures are considered to be adverse events if the abnormality:

- results in study withdrawal
- is associated with a serious adverse event
- is associated with clinical signs or symptoms
- leads to additional treatment or to further diagnostic tests
- is considered by the investigator to be of clinical significance

**Related** to the use of the drug: There is a reasonable possibility (more likely than not) that the experience may have been caused by the investigational drug.

A **serious adverse event** is any AE that is:

- fatal
- life-threatening
- requires or prolongs hospital stay
- results in persistent or significant disability or incapacity
- a congenital anomaly or birth defect
- an important medical event

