**SAE reporting timelines are defined as:**

- “24 Hour; 5 Calendar Days” – The SAE must initially be reported within 24 hours of learning of the SAE, followed by a complete SAE report within 5 calendar days of the initial 24 hour report.

Serious adverse events that occur more than 30 days after the last administration of investigational agent/intervention and have an attribution of possible, probable, or definite to dorgemeltucel-L require reporting on the same timelines as noted above.

Deaths clearly due to progressive disease should **NOT** be reported expeditiously but rather should be reported via routine reporting

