**Hospitalization, Prolonged Hospitalization or Surgery**

Any adverse event that results in hospitalization or prolonged hospitalization should be documented and reported as a serious adverse event unless specifically instructed otherwise in this protocol. Any condition responsible for surgery should be documented as an adverse event if the condition meets the criteria for and adverse event.

Neither the condition, hospitalization, prolonged hospitalization, nor surgery are reported as an adverse event in the following circumstances:

- Hospitalization or prolonged hospitalization for diagnostic or elective surgical procedures for a preexisting condition. Surgery should ***not*** be reported as an outcome of an adverse event if the purpose of the surgery was elective or diagnostic and the outcome was uneventful.
- Hospitalization or prolonged hospitalization required to allow efficacy measurement for the study.
- Hospitalization or prolonged hospitalization for therapy of the target disease of the study, unless it is a worsening or increase in frequency of hospital admissions as judged by the clinical investigator.

Routine Adverse Event Reporting

All Adverse Events must be reported in routine study data submissions. AEs reported through expedited SAE reports must also be reported in routine study data submissions (CRFs).

Adverse Event Case Report Form

All adverse events (regardless of grade and attribution) observed while on study and for 30 days after last dose of treatment, must be recorded on the adverse event case report form. After 30 days from last dose of treatment, only adverse events that are related to the study drug/combination are required to be recorded on the adverse event forms.

Reporting Requirements for Baseline Adverse Events:

A pertinent positive finding identified on baseline assessment is to be documented as a Baseline Adverse Event using CTCAE terminology and grade on the provided Baseline CRF. An expedited

AE report is not required if a patient is entered on to the study with a pre-existing condition (e.g., elevated laboratory value, diarrhea). The baseline AE must be re-assessed throughout the trial and reported if it fulfills expedited AE reporting guidelines.

- 1) If the pre-existing condition worsens in severity, the investigator must reassess the event to determine if an expedited report is required.

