**Safety Analyses**

Adverse events will be summarized by MedDRA system organ class and preferred term. Separate tabulations will be produced for all treatment-emergent adverse events, treatment-related adverse events (those considered by the Investigator as at least possibly drug related), serious adverse events, discontinuations due to adverse events, and adverse events of at least Grade 3 severity. By-patient listings will be provided for deaths, serious adverse events, and events leading to discontinuation of treatment.

Descriptive statistics will be provided for clinical laboratory data and vital signs data, presented as both actual values and changes from baseline relative to each on-study evaluation and to the last evaluation on study.

In addition, shift tables of laboratory data from baseline to worst value on treatment will be presented based on CTCAE v 4.03 grading.

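### Section 10.4 sets a higher bar for a related adverse event than the late-SAE rule in Section 10.6 and the table in Section 12.3, so late non-serious events judged only possible may go unrecorded

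*Combined protocol and SAP*

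**What the plan says.** **Section 10.4** gives the only definition of *related*: "There is a reasonable possibility (more likely than not", with causation by the investigational drug as the thing judged. The same section also attributes by precedent. An event already reported as related to one of the checkpoint inhibitors is assigned to that agent, and "Adverse events previously seen with dorgenmeltucel-L or other HyperAcute therapies will be attributed to dorgenmeltucel-L". Neither half of the precedent rule carries a probability.

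**Section 10.6** has several rules. Any SAE goes to the sponsor within 24 hours, whatever its cause. SAEs more than 30 days after the last administration that "have an attribution of possible, probable, or definite to dorgemeltucel-L require reporting on the same timelines". On the adverse event form, everything is recorded while the patient is on study and for 30 days after the last dose. After that, "only adverse events that are related to the study drug/combination are required to be recorded". A further list for long-term gene-transfer monitoring covers new malignancies, neurologic, autoimmune and hematologic disorders, unexpected illness, hospitalizations and deaths, with no test of causality.

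**Section 12.3 (Safety Analyses)** tabulates treatment-related adverse events as "those considered by the Investigator as at least possibly drug related".

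**The concern.** Read literally, *more likely than not* excludes an event that the investigator thinks possible but not probable. The late-SAE rule and the analysis section both include it, and nothing reconciles them.

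Two things follow. The first is labelling: two sites may see the same event, and one calls it related while the other does not. The second is capture: once 30 days have passed, the adverse event form depends on the word *related*, and an event that was never recorded cannot be recovered at analysis.

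Safety is a primary objective (synopsis and Section 1.1.1), and the trial is open-label (Section 12.2), so causality is judged with the treatment known. An unclear cut-off adds avoidable variation to that judgement.

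**Working it through.** No figure in the plan is at issue and no arithmetic decides the point. The check follows one event through each rule: an adverse event that the investigator judges possible, but not more likely than not, to be caused by treatment.

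| Rule | Place | Causality bar | Treatment of that event |
|---|---|---|---|
| Definition of *related* | 10.4 | above 50%; investigational drug only | unrelated |
| Precedent | 10.4 | none stated | attributed to an agent if the same kind of event is already known for it |
| Any SAE | 10.6, opening rule | none | reported if serious |
| Late SAE | 10.6, reporting timelines | possible or higher; dorgenmeltucel-L | reported if serious |
| AE form, up to 30 days | 10.6, AE case report form | none | recorded |
| AE form, after 30 days | 10.6, AE case report form | *related*, no cut-off given; study drug/combination | not required under 10.4; required if possible counts |
| Long-term list | 10.6, other reporting requirements | none | reported if of a listed kind |
| Treatment-related table | 12.3 | at least possible | counted, if labelled so and recorded |

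1. The first row contradicts the late-SAE and table rows. The conflict lies between stated rules, so it is not a case of missing detail.
2. Up to 30 days the conflict can change only the label, because every adverse event is recorded.
3. After 30 days the form rule needs a meaning for *related*, and Section 10.4 supplies the only one. The event then need not be recorded. If it is serious or on the long-term list, another rule picks it up. What remains exposed is chiefly non-serious events. A severe but non-serious event is among them, so the planned tabulation of Grade 3 or higher events could also lose entries.
4. *Possible* is a category that the sponsor has used. Section 2.3 reports that "Grade 1 events possibly related to the immunotherapy included fatigue, nausea, and dysgeusia", separately from injection-site reactions graded probably or definitely related.
5. The object of the definition also shifts. Section 10.4 speaks of the investigational drug, and the form rule speaks of the study drug or combination. The synopsis lists only dorgenmeltucel-L under investigational drugs, and Arm 2 does not receive it. The cut-off for checkpoint-inhibitor events, and so for all of Arm 2, is not clearly defined.

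**The case against.** The strongest reply is that Section 10.4 is not a bare test of more than 50%. Its precedent rule would attribute most familiar events without any probability judgement. Section 12.3 states its own cut-off, and the late-SAE rule implies a graded causality scale. If the CRF collects that scale, the related-event table can be built as specified. The CRF is not among the documents, so this cannot be excluded. The reply stands to this extent: the effect on the table is a risk of uneven labelling, not a demonstrated loss. It does not remove the point, because the precedent rule is a second test beside the first, with no statement of which prevails, and the late form rule still has no cut-off.

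Three stronger readings are tempting, and the documents do not support them.

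- *All adverse event capture after 30 days, and every safety table, depends on the definition.* SAEs and the long-term list have rules that do not use it. Section 12.3 also does not define the window for treatment-emergent events, so it is not settled which late events would enter that table.
- *The phase 1 summary in Section 2.3 shows four kinds of related event shrinking to one.* Fatigue, nausea and dysgeusia had been seen with dorgenmeltucel-L, so the precedent rule would attribute them to it. Section 5.1 also lists fatigue and nausea among the most frequent HyperAcute-related events.
- *The loss falls mainly on Arm 2A, from Day 94.* The fourth scheduled ipilimumab dose is on Day 64, and 64 + 30 = 94. Section 6.3, however, allows delayed doses up to 16 weeks from the first: Day 1 + 112 = Day 113, and 113 + 30 = 143. The form rule also covers the time on study, and the Arm 2A schema takes patients off study at progression, so the window may run longer still. Section 5.2 does say that a minority of ipilimumab reactions appear weeks to months after stopping, but such known reactions are also the ones that precedent would assign to ipilimumab.

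**Conclusion.** The conflict is real: *related* starts above 50% in Section 10.4, and at possible in the late-SAE rule and the Section 12.3 table. Its reach is limited to two effects. Sites may label the same event differently for the treatment-related table, and late, chiefly non-serious, possible events may be left off the adverse event form. Expedited SAE reporting, the long-term list and recording within 30 days are not affected, and the PFS analysis is untouched.

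The number of events cannot be estimated, because the documents give no distribution of causality categories. The conclusion assumes that sites take the meaning of *related* in the late form rule from Section 10.4, and that the CRF or its completion guide, which are not in the documents, do not already impose a different cut-off. With safety as a primary objective, the inconsistency should be corrected.

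**What to change.** - In Section 10.4, delete the parenthesis that sets the bar above 50%, and define *related* as possible, probable or definite. State that this covers dorgenmeltucel-L, the checkpoint inhibitors and the combination.
- Use that one cut-off in Section 10.6 for late SAE reporting and for recording on the adverse event form after 30 days, in the Section 12.3 table, and on the CRF.
- Add a sentence to Section 10.4 saying how attribution by precedent fits with the definition: whether it sets the causality category, or only names the agent once the investigator has judged the event related.

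The change is one of wording, plus a check of the CRF causality field. The price is that slightly more events are recorded late and counted as related.

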### ***10.5 Reporting Form and Content***

For those events that meet the criteria in Section 10.6 below, please complete the **Serious Adverse Event Reporting Form**. This form will be provided by NewLink Genetics. Please send to NewLink Genetics within the time frames listed below. Please FAX to [REDACTED] to [REDACTED]. Please call [REDACTED] with any reporting questions. You may also contact and send this form to the CRA designated for your site.

### ***10.6 Reporting Requirements for Serious Adverse Events (21 CFR Part 312)***

Investigators **MUST** immediately report to the sponsor **ANY** Serious Adverse Events within 24 hours of learning of the SAE, whether or not they are considered related to the investigational agent(s)/intervention (21 CFR 312.64)

**An adverse event is considered SERIOUS if it results in ANY of the following outcomes:**

1. Death
2. A life-threatening adverse event
3. An adverse event that results in inpatient hospitalization or prolongation of existing hospitalization for  $\geq 24$  hours
4. A persistent or significant incapacity or substantial disruption of the ability to conduct normal life functions
5. A congenital anomaly/birth defect.

6. Important Medical Events (IME) that may not result in death, be life-threatening, or require hospitalization may be considered serious when, based upon medical judgment, they may jeopardize the patient or subject and may require medical or surgical intervention to prevent one of the outcomes listed in this definition (FDA, 21 CFR 312.32; ICH E2A and ICH E6).

**SAE reporting timelines are defined as:**

- “24 Hour; 5 Calendar Days” – The SAE must initially be reported within 24 hours of learning of the SAE, followed by a complete SAE report within 5 calendar days of the initial 24 hour report.

Serious adverse events that occur more than 30 days after the last administration of investigational agent/intervention and have an attribution of possible, probable, or definite to dorgemeltucel-L require reporting on the same timelines as noted above.

Deaths clearly due to progressive disease should **NOT** be reported expeditiously but rather should be reported via routine reporting

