### **Specific Risk/Adverse Events with ipilimumab**

Ipilimumab can result in severe and fatal immune-mediated adverse reactions due to T-cell activation and proliferation. These immune-mediated reactions may involve any organ system; however, the most common severe immune-mediated adverse reactions are enterocolitis, hepatitis, dermatitis (including toxic epidermal necrolysis), neuropathy, and endocrinopathy. The majority of these immune-mediated reactions initially manifested during treatment; however, a minority occurred weeks to months after discontinuation of ipilimumab.

Permanently discontinue ipilimumab and initiate systemic high-dose corticosteroid therapy for severe immune-mediate reactions. Assess patients for signs and symptoms of enterocolitis, dermatitis, neuropathy, and endocrinopathy and evaluate clinical chemistries including liver function tests and thyroid function tests at baseline and before each dose. For specific details of toxicity management, the treating physician is instructed to refer to the package insert for ipilimumab and to follow the instructions and algorithms therein.

Specific attention to development of autoimmune events during periodic study visits can be evaluated by an optional checklist provided in **Appendix E**. This checklist in addition to the serologic tests obtained can be used by the study physicians to determine if further evaluation for autoimmune disease is warranted by an appropriate specialist in the organ system affected. This can be done to avoid misinterpretation of spurious autoimmune test results.

Trials using immunomodulatory agents such as ipilimumab CTLA-4 have shown a correlation between disease response and so called autoimmune breakthrough events (ABEs) like hypophysitis, colitis, autoimmune hepatitis, or dermatitis. It is for this reason that they are distinguished from other adverse events.

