### **Populations to be Analyzed**

The primary population for efficacy will be the full analysis set (FAS), defined as all randomized subjects. In the FAS patients will be analyzed in the treatment group to which they were assigned.

The primary population for safety analyses will be the safety analysis set, defined as all randomized subjects who receive at least one administration of study treatment (dorgenmeltucel-L or immune checkpoint therapy).

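### The late-SAE rule in Section 10.6 is tied to dorgenmeltucel-L, which Arm 2 never receives, so ascertainment of late safety events can differ by arm

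*Combined protocol and SAP*

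**What the plan says.** Four parts of the protocol bear on events after treatment ends.

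- **General SAE rule (Section 10.6, opening).** Investigators report every SAE to the sponsor within 24 hours, related or not. No end date is given.
- **Late-SAE sentence (Section 10.6, SAE reporting timelines).** It covers "Serious adverse events that occur more than 30 days after the last administration of investigational agent/intervention" that "have an attribution of possible, probable, or definite to dorgemeltucel-L require reporting on the same timelines as noted above".
- **AE form rule (Section 10.6, Adverse Event Case Report Form).** The form takes "All adverse events (regardless of grade and attribution) observed while on study and for 30 days after last dose of treatment". After that, "only adverse events that are related to the study drug/combination are required to be recorded on the adverse event forms".
- **Terms and attribution (Sections 10.4 and 12.3).** Section 10.4 states: "In this protocol the study drug dorgenmeltucel-L is being combined with one of three different immune checkpoint immunotherapies". It also directs that events already known for ipilimumab, nivolumab or pembrolizumab be attributed to those drugs. Section 12.3 uses a wider term when it defines the safety analysis set: "study treatment (dorgenmeltucel-L or immune checkpoint therapy".

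The Section 8 calendars for Arms 1A and 1C carry AE/SAE evaluation through study and follow-up. Those for Arms 2A, 2B and 2C mark it only to the first follow-up visit. After that visit, assessments other than imaging and survival checks follow standard of care.

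**The concern.** Section 1.1.1 makes the safety comparison of checkpoint inhibition alone with checkpoint inhibition plus dorgenmeltucel-L a primary objective. Such a comparison needs events to be found and recorded under the same rule in both arms. Here the rule written specifically for late SAEs depends on a product that only one arm receives.

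Late events are expected. Section 5.2 says of ipilimumab immune-mediated reactions that "a minority occurred weeks to months after discontinuation of ipilimumab". Section 11.3 lists unanticipated autoimmune disease as a theoretical risk of the vaccine. An Arm 1 investigator could therefore reasonably judge a late autoimmune SAE possibly related to dorgenmeltucel-L, and it would then fall under the late-SAE rule. The same event in Arm 2 cannot. If sites follow that sentence, late immune toxicity may be recorded unevenly, in the part of the safety profile where an interaction between vaccine and checkpoint inhibitor might appear.

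**Working it through.** The plan gives no figure for this point, so the check is mainly a comparison of passages, with one calculation of window length.

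**1. Events up to 30 days after the last dose.** All AEs are recorded whatever their attribution, in both arms. The rule itself does not differ by arm.

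**2. SAEs after 30 days, by arm and attribution.**

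| Late SAE | Late-SAE sentence | General SAE rule |
|---|---|---|
| Arm 2, attributed to checkpoint inhibitor | cannot be met | covered, if the rule has no end date |
| Arm 1, attributed to checkpoint inhibitor under Section 10.4 | not met | covered, if the rule has no end date |
| Arm 1, judged at least possibly related to the vaccine | met | covered |

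If the general rule ran without limit, the late-SAE sentence would add nothing, since its timelines are already set. It has a function only as a narrower rule after 30 days. The two therefore conflict, and the protocol does not say which governs.

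**3. Non-serious AEs after 30 days.** The condition is relation to the study drug or combination, which is not defined. With the Section 10.4 use of study drug (dorgenmeltucel-L), no Arm 2 event qualifies. With the Section 12.3 meaning of study treatment, checkpoint-related events qualify in both arms. This is an ambiguity rather than a stated exclusion.

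**4. Calendars.** The AE rows point the same way as the late-SAE sentence: through follow-up in Arms 1A and 1C, to the first follow-up visit in Arms 2A, 2B and 2C.

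**5. Length of the all-attribution window** (last scheduled dose day + 30), ipilimumab arms.

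- Immunizations in the Arm 1A schema: 14 to week 24, 6 monthly (months 7 to 12) and 4 quarterly (months 15 to 24). 14 + 6 + 4 = 24, which reproduces the calendar's stated maximum of 24.
- Arm 2A: last ipilimumab Day 64; 64 + 30 = Day 94.
- Arm 1A, all 24 immunizations given: with a 28-day month, 24 × 28 = 672 and 672 + 30 = Day 702. With a 30.4375-day month, 730.5 + 30 = Day 760.5. The month length is an assumption.
- Ratio: 702/94 = 7.5 to 760.5/94 = 8.1.
- Arm 1A, stopping at the Day 92 immunization: 92 + 30 = Day 122.

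In Arms 2B and 2C dosing continues to progression or significant toxicity, so their 30-day clock starts only then. The Day 94 figure also assumes that the 30-day limit closes the window. If being on study includes Arm 2A's observation period before progression, the window is longer.

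**The case against.** The strongest reply is that the late-SAE sentence contains no word of exclusion. It sits under a heading on timelines and can be read as setting expedited timing for one class of event, while the general rule still brings in every other SAE. Section 10.6 also asks that AEs leading to hospitalization be reported as serious, and its long-term follow-up list includes new autoimmune disorders and unexpected hospitalizations. The late-AE term can be read to include checkpoint inhibitors. Arm 2A patients are observed until progression, so events before progression may count as on study. Finally, Section 10.4 sends known checkpoint toxicities to the checkpoint inhibitor in Arm 1 as well, so the loss is not confined to Arm 2.

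Most of this stands, and it rules out stronger readings. A reader might infer that late toxicity in Arm 2 goes wholly uncaptured, or that the arms cannot be compared. The general SAE rule and the shared rule up to 30 days do not allow either. A reader might also assume that 2% to 10% of patients have a late related SAE, giving 50 × 0.02 = 1 to 50 × 0.10 = 5 control patients, and call that a spurious Arm 1 excess. That would need every late Arm 1 event to be attributed to the vaccine, against Section 10.4, and every Arm 2 event to go unreported, against the general rule. The rates have no source in the documents. Nor do the half-lives in Section 5 (14.7, 26.7 and 26 days) supply one: drug remaining at 30 days is not an event rate.

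What the reply does not do is reconcile the passages. The late-SAE sentence still names one product, it is redundant unless it narrows the general rule, and the long-term list is framed as gene-transfer monitoring, which Arm 2 patients do not need.

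**Conclusion.** The point holds as a conflict that can make late safety ascertainment differ by arm. No Arm 2 event can satisfy the late-SAE condition, the general SAE rule points the other way, and the late-AE term is unclear for Arm 2. Late checkpoint-related events are therefore not clearly required to be captured in Arm 2. In Arm 1, those attributed to the checkpoint inhibitor may also be missed, while those judged possibly related to the vaccine are reportable.

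Neither the size of any bias nor its realized direction can be derived from the documents. Both depend on how sites resolve the conflict and on an unknown late-event rate. The computable asymmetry is in window length: about 7.5 to 8 times longer in Arm 1A than in Arm 2A, if all immunizations are given and the 30-day limit closes the window. It shrinks when Arm 1A patients stop early. The protocol's statement on late onset concerns ipilimumab; extending it to the PD-1 inhibitors would be an assumption.

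**What to change.** - **One late-event rule.** Reconcile the general SAE rule, the late-SAE sentence and the AE form rule in Section 10.6. After 30 days from the last dose of any study treatment, require SAEs and AEs attributed to any study treatment, meaning dorgenmeltucel-L or the assigned checkpoint inhibitor, as in Section 12.3. Use that term throughout, state that it applies identically in both arms, and say whether the general SAE rule has an end date.
- **Calendars.** Extend the AE evaluation row for Arms 2A, 2B and 2C through follow-up, to match Arms 1A and 1C.
- **Analysis.** Rewording the attribution does not equalize the windows. In the safety analyses of Section 12.3, compare late events between arms over a common period from randomization, or adjust for length of observation.

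The cost is a short amendment and a few extra late SAE and AE forms. No dose or treatment rule changes.
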